## 15.2. Benefits and Risks: Clinical

Multiple Phase 2 and Phase 3 trials have now shown the potential benefit and safety of ataluren in the treatment nmCF in adults and children. Ataluren activity was demonstrated with TEPD testing in 2 separate Phase 2 trials (further details are provided in [Section 2.2](#)).

Clinical benefit was further explored in the multicenter Phase 3 double-blind study (Study 009). In this 48-week study positive trends favoring ataluren were seen in the primary endpoint, the relative change from baseline in %-predicted FEV1 at 48 weeks (-2.5% change on ataluren vs -5.5% change on placebo; p=0.124). An analysis of the relative change from baseline in %-predicted FEV1 across all post-baseline study visits demonstrated an average difference between ataluren and placebo of 2.5% (-1.8% average change on ataluren vs -4.3% average change on placebo; p= 0.0478). A larger effect was seen in the patients not receiving chronic inhaled antibiotics. The effect of inhaled antibiotics was largely attributable to the use of inhaled aminoglycosides (ie, tobramycin). In patients not receiving chronic inhaled tobramycin at baseline, the Week 48 difference between the ataluren and placebo arms in the relative change of %-predicted was 5.7% (-0.7% change on ataluren vs -6.4% change on placebo difference in FEV1).

The secondary endpoint, the rate of pulmonary exacerbations (ie, the number of pulmonary exacerbations in 48 weeks) also showed a positive trend in favor of ataluren, with the rate in the ataluren group being 23% lower than the placebo group (p=0.0992). In the patients not receiving chronic inhaled tobramycin, the pulmonary exacerbation rate in the ataluren group was 40% lower than the rate in the placebo group. These results show a consistent treatment effect of ataluren on both pulmonary function and exacerbation rates.

Collectively, the FEV1 and pulmonary exacerbation data, supported by TEPD results in the previous Phase 2 clinical trials, demonstrate the beneficial effect of ataluren in patients with

nmCF. Ataluren thus offers an important advance in the genetic-based treatment of nmCF in patients aged 6 years and older. The increased effect seen in patients not receiving chronic inhaled tobramycin makes benefit more likely in this subgroup, who will be enrolled in this study, further supports the potential for the benefit of ataluren therapy.

### **15.3. Benefits and Risks: Safety**

Safety results indicate that ataluren was generally well tolerated. Across all studies, the most common treatment-emergent adverse events were consistent with background CF-related sinus, pulmonary, or gastrointestinal symptoms. Notable in the Phase 2 and 3 trials was the occurrence of mild dysuria in several patients. Resolution was successfully achieved with increased hydration. No clearly dose-dependent increases in frequency or severity of adverse events were evident. There were no safety concerns identified in subjects' physical examinations, vital sign measurements, or electrocardiograms (ECGs).

In Study 009, the overall incidence of adverse events through Week 48 was similar in the ataluren and placebo groups. The most common adverse events were typical for CF and included pulmonary exacerbation, cough, and upper respiratory tract infection, which occurred at similar frequencies in the ataluren and placebo arms. Most of the serious adverse events, those requiring hospitalization, were pulmonary exacerbations unrelated to study treatment and some patients experienced creatinine elevations that occurred at Grades 3 and 4 in connection with concomitant treatment with systemic aminoglycosides (further details are provided in [Section 14.2.3.1](#)). Therefore, the Study 009 protocol was amended to prohibit the concomitant use of these antibiotics with ataluren, and to encourage patients to maintain adequate hydration. Non-serious episodes of creatinine elevation occurred predominantly in the ataluren arm and were transient, generally mild, and resolved with or without interruption of study medication.

In addition, clinical trials in nmDMD have demonstrated that the adverse-event profile of ataluren was comparable to that of placebo. In the double-blind study of nmDMD, six patients – all receiving corticosteroids - had hypertension (or increased blood pressure) reported as adverse events (0 for ataluren 20-, 20-, 40-mg/kg, 5 for ataluren 10-, 10-, 20-mg/kg, and 1 for placebo), although similar events were not seen in the nmCF studies. Mean total cholesterol and triglycerides were in the upper range of normal at baseline and increased, reaching borderline high or high values. The values tended to stabilize early in the study and did not increase further with continued treatment. Small increases in mean serum creatinine, BUN, and cystatin C were observed. Similarly, the values tended to stabilize early in the study and did not increase further with continued treatment.

Collectively, the safety data from clinical trials demonstrate that ataluren has a favorable safety profile for the treatment of patients with nmCF.

### **15.4. Benefit/Risk Conclusions**

Cystic fibrosis (CF) is a disabling and life-threatening genetic disorder resulting from mutations in the gene encoding the cystic fibrosis transmembrane conductance regulator (CFTR). CFTR dysfunction leads to multiple organ dysfunction starting in early childhood. An urgent unmet medical need exists for a therapy that addresses the underlying cause of nmCF, a condition for which no approved treatment exist. Ataluren 10-, 10-, 20-mg/kg represents the first disease-modifying therapy for this severely disabling, progressive, and, ultimately fatal disease.

The collective nonclinical and clinical data provide the basis for the continued development of ataluren treatment for nmCF. The clinical efficacy data, in addition to an overall generally favorable safety profile collected from Phase 2 and 3 clinical trials supports a positive benefit-risk profile to ataluren. Appropriate monitoring and laboratory evaluation, as detailed in [Section 14](#), is incorporated in this protocol in order to mitigate any risks to study participants. The current trial (Study 023) is feasible and will provide additional safety and efficacy data of ataluren in nmCF.

1. OVERVIEW

This statistical analysis plan (SAP) details the statistical methods to be used in the analyses and presentation of the data collected in Study PTC124-GD-023-CF (Study 023). Preparation of this SAP incorporates statistical design elements present in the study protocol version 3.0 (dated 03 February 2016). Where conflicts exist between this SAP and the study protocol, the information contained in this SAP supersedes the protocol. Any refinements to the SAP will be incorporated by amendment before the databases are locked.

2. STUDY OVERVIEW

2.1. Study Design

Study 023 is a Phase 3, international, multicenter, long-term safety study of ataluren in patients with nmCF that have completed participation in the double-blind study PTC124-GD-009-CF (Study 009).

It is planned that approximately 70 patients that completed participation in Study 009 will be enrolled into the study. All participating sites must therefore have had at least 1 patient that completed participation in Study 009. It is anticipated that most eligible patients would have also been enrolled in PTC124-GD-009e-CF (Study 009e), the 96-week open-label study that immediately proceeded Study 009. Eligible subjects will receive oral ataluren administered 3 times per day (TID) at respective morning, midday, and evening doses of 10-, 10-, and 20-mg/kg for ~192 weeks. The detailed schedule of assessments are displayed in [Table 1](#).

Planned interim safety analyses will be conducted by an independent data monitoring committee (DMC). The first safety review will occur when ~35 patients have completed ≥ 32 weeks of treatment. The second safety review will occur when ~35 patients have completed ≥ 64 weeks of treatment.

The study will be terminated prematurely according to company's strategic decision on March 2, 2017. All subject who are on-going by then will be discontinued.

Table 1. Schedule of Events

Study Period	Screening	Ataluren Treatment							
Study Week	Week -4 to -1	Week 1	Week 8 (Phone Call)	Week 16	Week 24 (Phone Call)	Week 32	Week 40 (Phone Call)	Week 48	Week 56 (Phone Call)
Study Day	-28 to -1	1 (+7 days)	56 (±7 days)	112 (±7 days)	168 (±7 days)	224 (±7 days)	280 (±7 days)	336 (±7 days)	392 (±7 days)
Visit / Call	1	2	2a	3	3a	4	4a	5	5a
Informed Consent	X								
IVR/IWR System Screening	X								
Clinical and Medication History	X								
Vital Signs (including pulse oximetry)	X	X		X		X		X	
Height	X	X		X		X		X	
Weight	X	X		X		X		X	
Physical Examination	X	As clinically indicated						X	As clinically indicated
Serum Viral Screen	X								
β-HCG ^a	X	X		X		X		X	
Cortisol, Renin, and Aldosterone	X	As clinically indicated							
Biochemistry ^b	X	X		X		X		X	
Hematology	X	X		X		X		X	
Urinalysis	X	X		X		X		X	
Ataluren PK (trough)				X		X		X	
Renal Ultrasound	X	As clinically indicated							
12-Lead ECG	X			X		X		X	
Ataluren Administration in Clinic		X ^c							
Ataluren Dispensation		X		X		X		X	
Review Ataluren Compliance				X		X		X	
Adverse Events	X ^d	X		X		X		X	
Concomitant Medication / Non-Drug Therapy	X	X		X		X		X	
Spirometry	X	X		X		X		X	
Respiratory Event Evaluation ^c	X	X	X	X	X	X	X	X	X
Presence of P. aeruginosa in Sputum	X	X		X		X		X	

Table 1. Schedule of Events - Continued

Study Period	Ataluren Treatment									
	Study Week	Week 64	Week 72 (Phone Call)	Week 80	Week 88 (Phone Call)	Week 96	Week 104 (Phone Call)	Week 112	Week 120 (Phone Call)	Week 128
Study Day	448 (+7 days)	504 (±7 days)	560 (±7 days)	616 (±7 days)	672 (±7 days)	728 (±7 days)	784 (±7 days)	840 (±7 days)	896 (±7 days)	952 (±7 days)
Visit / Call	6	6a	7	7a	8	8a	9	9a	10	10a
Vital Signs (including pulse oximetry)	X		X		X		X		X	
Height	X		X		X		X		X	
Weight	X		X		X		X		X	
Physical Examination	As clinically indicated				X	As clinically indicated				
Serum Viral Screen										
β-HCG ^a	X		X		X		X		X	
Cortisol, Renin, and Aldosterone	As clinically indicated									
Biochemistry ^b	X		X		X		X		X	
Hematology	X		X		X		X		X	
Urinalysis	X		X		X		X		X	
Ataluren PK (trough)	X		X		X		X		X	
Renal Ultrasound	As clinically indicated									
12-Lead ECG	X		X		X		X		X	
Ataluren Administration in Clinic										
Ataluren Dispensation	X		X		X		X		X	
Review Ataluren Compliance	X		X		X		X		X	
Adverse Events	X		X		X		X		X	
Concomitant Medication /										

Non-Drug Therapy	X		X		X		X		X	
Spirometry	X		X		X		X		X	
Respiratory Event Evaluation ^c	X	X	X	X	X	X	X	X	X	X
Presence of P. aeruginosa in Sputum	X		X		X		X		X	

Table 1. Schedule of Events - Continued

Study Period	Ataluren Treatment							4-Week Post-Treatment Follow-Up (End of Study)
	Study Week	Week 144	Week 152 (Phone Call)	Week 160	Week 168 (Phone Call)	Week 176	Week 184 (Phone Call)	
Study Day	1008 (±7 days)	1064 (±7 days)	1120 (±7 days)	1176 (±7 days)	1232 (±7 days)	1288 (±7 days)	1344 (±7 days)	1372 (±7 days)
Visit / Call	11	11a	12	12a	13	13a	14	15
Vital Signs (including pulse oximetry)	X		X		X		X	X
Height	X		X		X		X	X
Weight	X		X		X		X	X
Physical Examination	X	As clinically indicated					X	X
Serum Viral Screen								
β-HCG ^a	X		X		X		X	X
Cortisol, Renin, and Aldosterone		As clinically indicated						
Biochemistry ^b	X		X		X		X	X
Hematology	X		X		X		X	X
Urinalysis	X		X		X		X	X
Ataluren PK (trough)	X		X		X		X	
Renal Ultrasound		As clinically indicated						
12-Lead ECG	X		X		X		X	X

Ataluren Administration in Clinic								
Ataluren Dispensation	X		X		X			
Review Ataluren Compliance	X		X		X		X	
Adverse Events	X		X		X		X	X
Concomitant Medication / Non-Drug Therapy	X		X		X		X	X
Spirometry	X		X		X		X	X
Respiratory Event Evaluation ^e	X	X	X	X	X	X	X	
Presence of P. aeruginosa in Sputum	X		X		X		X	

^a Testing for female subjects only.

^b Ideally, subjects should have fasted for at least 8 hours prior to blood collection.

^c Clinic staff will administer the first dose of study drug at Study Day 1 (Visit 2).

^d Adverse events (AEs) should be elicited from subjects at all study visits; however, any untoward medical occurrences collected at Screening will be used to assess study eligibility only and will not be reported as AEs in the CRF.

^e Includes completion of the Respiratory Event Form (REF).

^f Patients that do not complete ≥ 192 Weeks of treatment will be considered prematurely discontinued.

Abbreviations: β -HCG = human chorionic gonadotropin, D/C = discontinuation, ECG = electrocardiogram, EOT = end of treatment, IVR/IWR = Interactive Voice Response/Interactive Web Response, PK = pharmacokinetic

2.2. Study Objectives

2.2.1. Primary Objective

The primary objective of this study is to determine the long-term safety and tolerability of 10-, 10-, 20- mg/kg ataluren in patients with nmCF who completed participation in the double-blind study (PTC124-GD-009-CF) as assessed by adverse events and laboratory abnormalities.

2.2.2. Secondary Objectives

The secondary objectives are to determine the efficacy and safety of ataluren as assessed by spirometry (FEV₁), pulmonary exacerbation rate, and other safety parameters (eg, 12-lead ECG measurements, vital signs).

2.2.3. Tertiary Objectives

The tertiary objectives are to determine the efficacy of ataluren as assessed by other parameters of pulmonary function (FVC and FEF₂₅₋₇₅), and changes in body weight BMI.

2.3. Study Endpoints

2.3.1. Primary Endpoint

- Safety profile characterized by type, frequency, severity, timing, and relationship to ataluren of any adverse events, and laboratory abnormalities

2.3.2. Secondary Endpoints

- Change from baseline to end of treatment in spirometric performance as measured by FEV₁
- Rate of pulmonary exacerbations, as assessed by modified Fuchs (primary definition), Fuchs and expanded Fuchs criteria
- Change from baseline in other safety parameters (eg, 12-lead ECG measurements, vital signs)

2.3.3. Tertiary Endpoints

- Change from baseline to end of treatment in spirometric performance as measured by FVC and FEF₂₅₋₇₅
- Change from baseline to end of treatment in body weight and BMI

2.3.4. Other Endpoints

- Study drug extent of exposure and characterization of investigator-prescribed dosing modifications

- Study drug compliance as assessed by a subject daily diary and by quantification of used and unused study drug
- Incidence of concomitant therapies

2.4. Sample Size

Approximately 70 patients that completed participation in Study 009 will be enrolled into the study. The sample size is not determined by statistical power.

3. STUDY POPULATIONS

3.1. As-Treated Population

The As-Treated population consists of all subjects who received at least 1 dose of ataluren. This population will be evaluated in the analyses of safety and treatment administration.

3.2. Intention-to-Treat (ITT) Population

The Intention-to-Treat (ITT) population consists of all subjects who have at least 1 post-baseline efficacy assessment. This population will be evaluated in the analysis of efficacy.

4. STATISTICAL AND ANALYTICAL PROCEDURES

4.1. General Statistical Considerations

By-subject listings will be created for each CRF module. Summary tables for continuous variables will contain the following statistics: n, mean, standard deviation, standard error, and 95% confidence intervals (CIs) on the mean, median, minimum, and maximum. Summary tables for categorical variables will include N, n, percentage, and 95% CIs on the percentage. Where applicable, the summary data (mean, standard error) will be presented in graphical form by time of visit.

The baseline value used in each analysis will be the last (most recent) non-missing pretreatment value, except as noted for spirometry data.

Unless otherwise specified, all applicable analyses will be 2-sided at the 0.05 level of significance.

All analyses and tabulations of data will be performed using SAS (Version 9.1 or higher).

4.2. Control of the Multiplicities

Since all analyses are descriptive in this study, there is no need to control the multiplicity.

4.3. Missing Data Handling

In general, the missing data in safety endpoints will not be imputed, unless specified otherwise. The imputation rules of missing start/stop dates in adverse events and prior/concomitant medications/therapies will be documented in Section 5.5.

4.4. Multiple Centers

Study centers from different countries will be pooled by geographic region (North America [US and Canada], Europe, and Other [ie, Australia, Israel, Argentina, and Brazil]). The number of subjects in each region will be reported.

4.5. Subject Disposition

4.5.1. Accounting for Subjects

Subject enrollment status will be summarized by country and site for the As-Treated population. The number and percentage of subjects will also be reported by all enrolled subjects, the ITT population, and the As-Treated population. The number of subjects at each scheduled visit will be tabulated for the As-Treated population. For the As-Treated population, the number of completers, subjects who discontinue prematurely from the study, and reasons of discontinuation will be tabulated. In addition, reasons of screening failures will be summarized and listed.

4.5.2. Protocol Deviations

All major protocol deviations will be summarized by type for the ITT population. A listing of major and minor protocol deviations will be provided.

4.6. Demographics and Baseline Characteristics

Subject demographics and baseline characteristics will be summarized for ITT and As-Treated populations.

The continuous baseline characteristics include age (years), baseline height (cm), baseline weight (kg), baseline BMI (kg/m^2), %-predicted FEV₁ at screening and baseline. The categorical baseline characteristics include gender, race, region, age group (<18 vs \geq 18 years), baseline %-predicted FEV₁ group (<65% vs \geq 65%), presence of pancreatic insufficiency, chronically infected *Pseudomonas aeruginosa*, and diabetes in medical history.

4.7. Medical History

The medical history will be summarized by the system organ class and preferred term. The listing of medical history will be provided as well.

4.8. Prior and Concomitant Medications and Procedures

Prior medications will be defined as those medications that were used prior to the first dose of study treatment. Concomitant medications will be defined as those medications that were used during the study treatment period. If the start date of a medication is missing and the end date is

prior to study start, the medication will be deemed prior. If the end date is after study start or is also missing, the drug will be deemed concomitant. If the end date is missing or the medication is ongoing, the medication will be considered concomitant. If the medication start date is completely missing and end date is missing or ongoing, the medication will be considered both prior and concomitant. Prior and concomitant therapies will be defined similarly.

Prior and concomitant medications will be coded by means of the World Health Organization Drug Dictionary (WHODRUG) into Anatomical-Therapeutic-Chemical classification (ATC) codes. Subject incidence of prior and concomitant medications will be tabulated by ATC level 2 and preferred term for the As-Treated population. Subjects will only count once for each ATC or preferred term in the event that they have multiple records of the same ATC or preferred term in the database.

Prior and concomitant non-drug therapies will be coded and analyzed similarly.

4.9. Study Treatment Administration and Compliance

The study treatment duration in weeks is defined as $(\text{last dose date} - \text{first dose date} + 1)/7$ and will be summarized overall. This duration is irrespective of the dose interruptions.

The drug compliance of a specific time period is defined as $100 * (\text{number of sachets taken during the period} / \text{number of planned sachets during the period})$. It will be summarized for overall treatment duration. The percentages will take into account physician-prescribed reductions and interruptions.

The number and percentage of subjects having dose interruptions and dose changes will be summarized using descriptive statistics for overall treatment duration.

The above analyses will be performed for the As-Treated population.

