### **6.1.3. Study Drug Dispensation**

Dosing of ataluren will be based on milligrams of drug per kilogram of subject body weight at Screening (Visit 1) and will be calculated to allow for dosing with 1 or 2 of the 3 available sachet dose strengths (125- or 250- or 1000-mg of ataluren).

The clinic staff (eg, pharmacist or other qualified person) will be responsible for dispensing ataluren in 16-week increments according to the dosing schedule and IVR/IWR directions.

Because of potential changes in subject body weight over time, at Week 32 (Visit 4), Week 64 (Visit 6), Week 96 (Visit 8), Week 128 (Visit 10) and Week 160 (Visit 12) a dose adjustment may be made based on the subject's body weight at that visit. Depending upon the magnitude of change in subject body weight since baseline, the number and strengths of sachets to be used by the subject may remain the same or may be adjusted.

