### **6.2. Study Drug Treatment**

#### **6.2.1. Study Drug Dosing**

Dosing of ataluren will be based on milligrams of drug per kilogram of subject body weight at Screening (Visit 1). All subjects will receive approximately 10-, 10-, 20-mg/kg ataluren TID for ~192 weeks. At Week 32 (Visit 4), Week 64 (Visit 6), Week 96 (Visit 8), Week 128 (Visit 10) and Week 160 (Visit 12) dose adjustment may be made based on the subject's body weight at that visit.

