### **6.3.3. Instructions for Resuming Ataluren Administration after an Interruption for Safety Concerns**

In deciding whether to re-institute ataluren after a dose interruption for any clinically significant safety concern, the investigator should consider factors such as the following:

- Type and severity of the adverse event or laboratory abnormality
- The potential causal relationship of ataluren
- The subject's status in terms of CF and other health conditions
- The ability to monitor for recurrence of the event

For hepatic or renal events (refer to [Table 2](#)), the level of investigator certainty that an abnormality leading to drug interruption is drug-related should be considered strongly in deciding whether or not to re-institute ataluren treatment. If the investigator considers the hepatic or renal event that led to ataluren interruption to be probably related to ataluren, restarting ataluren is not advised. In this case, the subject should be discontinued from the study (see [Sections 6.3.4](#) and [10](#)). If the investigator considers the hepatic or renal event that prompted ataluren interruption to be possibly related or unlikely related to ataluren, the investigator should use best judgment in determining whether to restart ataluren. If the hepatic or renal event is considered unrelated to ataluren, re-institution of ataluren is recommended.

If the investigator believes it is appropriate to do so and the PTC Therapeutics medical monitor has been consulted, ataluren may be re-initiated. If the event was determined to be unrelated to ataluren, the treatment may be resumed at full dose. Otherwise, if the drug is resumed, it should be initially re-initiated at half of the original dose. The appropriate clinic staff should instruct the subject/caregiver about the revised number of study drug sachets to be used per dose according to the new schedule. Re-challenge at half dose should be initiated only as a bridge to full dosing. If a subject cannot tolerate the full dose, they should be discontinued from study participation.

If further evaluation reveals that the adverse event that led to dose reduction was not related to the ataluren, the dose should be escalated to the original dose level. The appropriate clinic staff should instruct the subject/caregiver about the revised number of ataluren sachets to be used per dose according to the schedule provided by the IVR/IWR system.

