### **7.1.2. Therapy for CF Pulmonary Exacerbations or Other CF Complications**

Subjects should receive appropriate antibiotic or other therapy for CF pulmonary exacerbations or other CF-related complications (eg, DIOS) consistent with local best practices and guidelines. For subjects requiring systemic antibiotic therapy, IV aminoglycosides may be used when medically necessary. However, given ataluren's ribosomal mechanism of action, and the possibility of aminoglycosides exhibiting a confounding effect upon study results, investigators should substitute other antibiotics for systemic aminoglycosides in subjects who require treatment for serious infections whenever possible. For such severe infections, consideration should be given to use of appropriate alternative anti-pseudomonal agents including macrolide and glycopeptide antibiotics. Subjects requiring IV therapy with a glycopeptide antibiotic (eg, vancomycin), should be closely monitored in an appropriate setting, such as a hospital. Based on the increased incidence of creatinine elevation in patients treated with IV aminoglycosides and/or vancomycin, concomitant use of these medications with ataluren is contraindicated. If nephrotoxic antibiotics (eg, tobramycin or vancomycin) are administered, ataluren treatment must be interrupted for the duration of IV antibiotic treatment. In subjects receiving any type of potentially nephrotoxic agents, antibiotic drug levels, and renal function should be closely monitored. Creatinine and BUN should be measured prior to initiating aminoglycosides or other potentially nephrotoxic therapy, and at least twice a week during the course of such antibiotic treatment, where possible. The antibiotic trough level, creatinine and BUN should be measured within 24 to 48 hours of administration of the first antibiotic dose, and further antibiotic dosing should be based on these results. Trough levels should also be measured at intervals during the course of antibiotic treatment, where possible. Additionally, subjects should be adequately hydrated prior to receiving potentially nephrotoxic IV antibiotics, and hydration status should be carefully monitored throughout the administration of these agents. Investigators should be particularly vigilant with subjects experiencing nausea, vomiting, diarrhea, fever, or laboratory evidence of dehydration. Treatment with ataluren may be resumed no earlier than 2 days after administration of nephrotoxic antibiotics has ceased.

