### **11.4.3. Study Treatment Administration**

For each subject, ataluren administration will be described, inclusive of duration of therapy, dose modifications, dose delays and omissions, and reasons for any deviations from planned therapy.

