#### **14.1.2. Inclusion of Minors**

Inclusion of both children and adults in this protocol is appropriate and necessary. Based on past experience in multiple randomized clinical trials [[Fuchs 1994](#), [Ramsey 1999](#), [Saiman 2003](#), [Elkins 2006](#)], including the double-blind study of ataluren in nmCF [[Rowe 2012](#)], there is strong precedence for this approach. The benefit-risk ratio is enhanced by inclusion of only children with FEV1 values ≤ 90% of predicted, weighting enrollment toward those who are already experiencing CF-related pulmonary compromise. In addition, this ratio is enhanced by the known severity of the disease phenotype in patients with CF caused by nonsense mutations [[Shoshani 1992](#), [Cystic Fibrosis Genotype-Phenotype Consortium 1993](#), [Kerem 1996](#), [de Gracia 2005](#), [McKone 2006](#)], the generally favorable safety profile of ataluren, and the limited

population of patients with nonsense-mutation-mediated disease (10% of the total CF population).

Inclusion of children as well as adults will allow an understanding of how age-dependent disease characteristics may affect treatment outcomes. A total of 65 (86.7%) patients <18 years of age completed Study 009 and are eligible for this open-label extension study. Participation of these younger patients in this extension study will allow further exploration of the influence of age on safety and efficacy outcomes. Study participants will now be at least 9 years of age, enhancing the ability of participants to reliably perform protocol procedures [Loeb 2008] and will have nomogram data describing %-predicted FEV1 values [Wang 1993].

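### SAP 4.9 summarises dose interruptions and dose changes without reasons and leaves *dose change* undefined, so safety-driven modifications cannot be told apart from weight adjustments and mandated antibiotic interruptions

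*SAP*

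**What the plan says.** SAP 4.9 (Study Treatment Administration and Compliance) states: "The number and percentage of subjects having dose interruptions and dose changes will be summarized using descriptive statistics for overall treatment duration". Neither *dose change* nor *dose interruption* is defined there or elsewhere in the SAP, and no reason category is given.

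The protocol provides several routes to a change or an interruption:

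- **Weight.** Protocol 6.2.1 says that a "dose adjustment may be made based on" body weight at Weeks 32, 64, 96, 128 and 160. Protocol 6.1.3 adds that the number and strength of sachets may then stay the same or be altered.
- **Nephrotoxic antibiotics.** Protocol 7.1.2 says that, when these are given, "ataluren treatment must be interrupted for the duration of IV antibiotic treatment".
- **Safety.** Protocol 6.3.1 and its Table 2 set laboratory thresholds for stopping drug. Protocol 6.3.3 says of a restart after an event not judged unrelated that "it should be initially re-initiated at half of the original dose", as a bridge back to the full dose.

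For the analysis of treatment administration, Protocol 11.4.3 asks for a description by subject that includes "reasons for any deviations from planned therapy". SAP Section 6, which records analysis changes from the protocol, does not mention this item.

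**The concern.** Safety and tolerability form the primary objective, and Protocol 14.2.8 treats interruption as the first response to an adverse finding. How many subjects had drug held or reduced for safety is therefore a natural question for the final report. SAP 4.10.1 tabulates treatment-emergent adverse events leading to permanent discontinuation, but none leading to interruption or reduction. The SAP 4.9 summary is the only planned table that would capture temporary stops and reductions.

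As specified, that summary cannot answer the question. A child who moves up a sachet strength after growing and a subject restarted at half dose can both appear as having a dose change. A subject whose drug was held because the protocol requires it during IV tobramycin and one stopped for a Table 2 transaminase value can both appear as having an interruption. The antibiotic distinction matters here. Protocol 14.2.3.1.1 reports that all 7 renal-dysfunction serious events in Study 009 came with nephrotoxic antibiotics, and SAP 4.10.1 already lists renal events separately by use of such drugs.

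**Working it through.** The documents give no figure for this summary, so there is nothing to reproduce. The check is mainly a comparison of text.

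**1. What falls under the SAP's words**

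| Cause | Source | Appears under | Safety-driven? |
|---|---|---|---|
| Scheduled weight adjustment | Protocol 6.1.3, 6.2.1 | dose change | no |
| Hold during nephrotoxic IV antibiotics | Protocol 7.1.2 | interruption | required by protocol |
| Stop for a Table 2 value or adverse event | Protocol 6.3.1 | interruption | yes |
| Half-dose restart | Protocol 6.3.3 | dose change | yes |
| Return to full dose | Protocol 6.3.3 | dose change | follows a safety reduction |

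The compliance paragraph of SAP 4.9 speaks of reductions and interruptions prescribed by the physician. The next paragraph uses the wider term *dose changes*. Nothing in the section excludes the first two rows. Whether the sentence yields one line or two (interruptions, changes), each line can hold both kinds of cause.

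**2. Whether reasons are picked up elsewhere**

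- SAP 4.10.1: discontinuation tables only; none for interruption or reduction.
- SAP 4.1: listings by subject for every CRF module. Reasons could appear there, but not as a summary.
- SAP 2.3.4: an additional endpoint on characterising modifications ordered by the investigator. The only analysis that serves it is the SAP 4.9 count.
- SAP Section 6: the removals listed are time of withdrawal, the paired t-test on FEV1 and the FEF25-75 summary. Reasons for dose deviations are not listed.

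**3. Can the number of weight-driven changes be derived?**

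No. The smallest sachet is 125 mg (Protocol 6.1), so one might take 125/20 = 6.25 kg as the gain that moves the 20 mg/kg evening dose one step. That needs every multiple of 125 mg to be available. Protocol 6.1.3 uses one or two of the three strengths (125, 250, 1000 mg). If this means at most two sachets, nothing lies between 250 + 250 = 500 mg and 1000 mg, and that step is (1000 − 500)/20 = 25 kg. The rounding rule, the age mix and the weights are not given. All that is known is "Study participants will now be at least 9 years of age" (Protocol 14.1.2), so growth is plausible but unquantified. SAP 2.1 also records early termination, so the later weight checks may not have taken place.

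**4. Illustration only (every rate below is an assumption)**

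Share with at least one weight-driven change over k checks, each with chance p: 1 − (1 − p)^k.

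| p | k = 5 | k = 2 |
|---|---|---|
| 0.05 | 23% | 10% |
| 0.10 | 41% | 19% |
| 0.20 | 67% | 36% |
| 0.30 | 83% | 51% |

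Let t be the safety share, w the weight share and a the antibiotic share, independent of one another. The pooled share is 1 − (1 − t)(1 − w)(1 − a). With t = 5% of 70 = 3.5 subjects:

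- w = 10%, a = 10%: 1 − 0.95 × 0.90 × 0.90 = 23%, about 16 of 70.
- w = 60%, a = 30%: 1 − 0.95 × 0.40 × 0.70 = 73%, about 51 of 70.

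Two separate lines do not cure this. With t = 5% on the interruption line, a of 10% to 30% gives 1 − 0.95 × 0.90 = 14.5% to 1 − 0.95 × 0.70 = 33.5%, or about 10 to 23 of 70.

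**The case against.** The strongest reply is that SAP 4.9 is a treatment-administration summary outside the primary analyses, and that the primary objective says tolerability is assessed by adverse events and laboratory abnormalities. A reader might infer that the trial's tolerability result is itself contaminated. The documents do not support that, because no section designates this count as the tolerability measure. This part of the reply stands.

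Second, the pooling is inferred from silence. SAP 2.3.4 refers to modifications ordered by the investigator, which might leave out scheduled weight adjustment. This also stands, but it shows that the term needs a definition.

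Third, a reader might infer that the SAP has dropped the reasons. That is not shown. SAP Section 1 lets the SAP override the protocol only where the two conflict, and silence is not conflict. Protocol 11.4.3 asks for a description by subject, which listings could meet. A weight adjustment may also count as planned therapy, not a deviation from it. What can be said is that the SAP's summary does not carry the reasons and Section 6 declares no change.

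Fourth, a reader might conclude that the dose-change percentage would mainly measure growth. The documents give no age mix, weights or rounding rule for this study, so that cannot be established.

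Finally, much toxicity is covered elsewhere: Table 2 categories by worst grade (SAP 4.10.2), events leading to discontinuation, and events of Grade 3 or higher (SAP 4.10.1). What remains uncovered is temporary interruptions and reductions.

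**Conclusion.** The point holds as a gap in one supportive summary. SAP 4.9 leaves *dose change* undefined and splits neither changes nor interruptions by reason. In the ordinary sense of its words it can mix scheduled weight adjustments and mandated antibiotic interruptions with safety-driven interruptions and half-dose restarts. No other planned table separates them.

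Its reach is limited. The primary adverse-event and laboratory analyses and the permanent-discontinuation tables do not depend on it, and no decision rule uses it. The number of subjects affected cannot be derived from the documents. The illustrative range shows only that a small safety-driven count could be hidden in a larger one. The conclusion rests on the ordinary meaning of *dose change* and *dose interruption*; if the sponsor intends a narrower meaning, the SAP should say so. This is a cheap improvement, not an error that undermines the trial's conclusions.

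**What to change.** Amend SAP 4.9 before database lock, as SAP Section 1 allows:

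1. Define *dose change*, and state whether scheduled weight adjustments count.
2. Tabulate dose changes by recorded reason: scheduled weight adjustment, safety reduction, re-escalation, other.
3. Tabulate interruptions by recorded reason: adverse event or Table 2 laboratory value, nephrotoxic antibiotic, other. Let a subject appear under more than one reason.
4. Report the number and percentage of subjects with at least one safety-driven interruption or reduction, labelled as a supportive tolerability summary.

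The cost is SAP wording and one extra table classification. It relies on reasons being recorded in the CRF, as Protocol 11.4.3 presupposes; Protocol 9.3 also has the action taken recorded for each adverse event. No visit, procedure or dosing rule changes.
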